10 MEASUREMENT OF EFFECT

10.1 Evaluation Of Response

10.1.1 Imaging Response

Response to therapy and/or progression after induction chemotherapy with FOLFIRINOX will be evaluated in this study using the international criteria proposed by the RECIST (Response Evaluation Criteria in Solid Tumors) committee. Changes in only the largest diameter (unidimensional measurement) of the tumor lesions are used in the RECIST criteria. In the event that CT staging cannot be utilized, restaging MRI will be the substitute modality.

10.1.2 Pathological Response

All patients will undergo a full pathological review of their pancreaticoduodenectomy specimen according to the AJCC Staging Classification, 6th. Initial gross evaluation and identification of resection margins will be performed jointly by the surgeon and the pathologist. Pathological complete response will be defined as the absence of any viable tumor cells within the pathologic specimen.

10.1.3 Progression-free survival

Progression-free survival will be defined as the time from date of protocol entry to first objective documentation of progressive disease (distant or local) or death. Patients who die without a reported prior progression will be considered to have progressed on the day of their death.

10.1.4 Time to death

Time to death will be calculated as the time from date of protocol entry to date of death

10.1.5 Time to local recurrence

A local recurrence will be defined as any evidence of tumor recurrence within the radiation field. The time to local recurrence will be calculated from the date of protocol entry to the first objective documentation of a local recurrence.

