2.2.5 Proton-based Short Course Radiation Therapy for pancreatic cancer: MGH Experience

The safety and efficacy of a one-week course of preoperative proton beam therapy and capecitabine followed by early pancreaticoduodenectomy (PD) was explored in a prior study in our institution in a different study population. Patients with radiographically resectable, biopsy-proven pancreatic cancer of the head of the pancreas were enrolled from May 2007-March 2010 on this IRB-approved, NCI-sponsored clinical trial. Eligibility included no CT involvement of the SMA or celiac arteries; adequate renal, hepatic and hematopoietic function; and ECOG Performance Status 0/1. Dose level 1 consisted of Proton Beam Therapy delivered 3 Gy x 10 Monday to Friday. Patients in subsequent dose levels received 5 Gy x 5 in progressively shortened schedules: level 2 (week 1 Monday, Wednesday, Friday, week 2 Tuesday, Thursday),

level 3 (week 1 Monday, Tuesday, Thursday, Friday, week 2 Monday), level 4 (week 1 Monday-Friday). Proton beam therapy was targeted at pancreatic mass with elective nodal coverage. Patients received Capecitabine 825 mg/m² BID weeks 1 and 2 Monday-Friday. Surgery was performed 1-6 weeks after completion of chemotherapy. Patients were recommended to receive 6 months of gemcitabine after surgery. 31 patients were enrolled on study. 27 patients are eligible for this analysis. Three patients were treated at each of dose levels 1-3. Six patients were at dose level 4, which was selected as the MTD. No dose limiting toxicities were observed. There were no unexpected 30-day post-op complications noted in comparison to historical controls. Four of 21 resected patients had positive margins. 17/21 had positive nodes. Median follow up is 10 months. There have been 2 local failures/progression in ALL patients, both with synchronous metastatic disease (at 10 months and 17 months). Metastatic failure has occurred in 15 out of 27 patients (56%). In summary, we found pre-operative Chemo Radiation Therapy with 1 week of Proton Beam Therapy and capecitabine followed by early surgery feasible and associated with satisfactory local control.

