14.4 Analysis of Secondary Endpoints

Progression-free survival: All patients who start the protocol therapy will be analyzed based on the definition in Section 10.1.3. The Kaplan-Meier method will be used to estimate progression-free survival with 90% confidence intervals constructed by Greenwood's formula.

Overall survival: Overall survival will be defined as the duration between the dates of protocol enrollment and death. The survival time of patients who are not known to have died will be censored at the date they were last known to be alive.

Toxicity: All patients who begin protocol treatment will be included in the toxicity profile. Toxicity summaries will include the frequency and proportion of patients experiencing each type of toxicity, as well as summaries by toxicity category and grade.

Surgical morbidity: Analysis will be based on the patients who undergo pancreaticoduodenectomy or distal pancreatectomy. The surgical morbidity rate will be calculated as the proportion of patients who experience peri- and post-operative complications within 30 days of surgery. A 90% confidence interval will be obtained using the exact binomial distribution.

30-day post-operative mortality rate: Analysis will be based on the patients who undergo pancreaticoduodenectomy or distal pancreatectomy. The 30-day post-operative mortality rate will be calculated as the number of patients who die within 30 days of surgery. A 90% confidence interval will be obtained using the exact binomial distribution.

Pathologic downstaging: Analysis will be based on the patients who undergo pancreaticoduodenectomy or distal pancreatectomy. The pathologic downstaging rate will be calculated as the proportion of patients with the primary tumor and nodes downstaged based on final pathology of the surgical specimen.

Local control rate: Local control will be defined as the time from protocol enrollment to the first objective documentation of local failure. Patients who have not experienced a local failure will be censored at the last date they were known to have local control. Kaplan-Meier methodology will be used to estimate the local control rate.

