14.5 Reporting and Exclusions

All patients who begin protocol treatment will be included in the analysis of all the primary and secondary endpoints, except for the surgical outcomes as noted in 14.4.

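### The only definition of a local event requires a radiation field, yet local control is timed from enrollment in all treated patients, so local progression before radiation is censored and not counted

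*Combined protocol and SAP*

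**What the plan says.** Objective 1.3.7 is the local control rate with FOLFIRINOX plus preoperative short-course radiation. Four parts of the protocol determine how it is measured.

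- **Event (10.1.5).** "A local recurrence will be defined as any evidence of tumor recurrence within the radiation field".
- **Clock (10.1.5).** "The time to local recurrence will be calculated from the date of protocol entry to the first objective documentation of a local recurrence".
- **Analysis (14.4).** "Local control will be defined as the time from protocol enrollment to the first objective documentation of local failure". Patients without the event are handled as follows: "Patients who have not experienced a local failure will be censored at the last date they were known to have local control". The estimator is Kaplan-Meier: "Kaplan-Meier methodology will be used to estimate the local control rate".
- **Analysis set (14.5).** "All patients who begin protocol treatment will be included in the analysis of all the primary and secondary endpoints", with an exception only for the surgical outcomes. Local control is not among those in 14.4 that are limited to resected patients.

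Section 14.4 uses the term local failure without defining it and without citing 10.1.5. Its entry for progression-free survival (PFS) does cite 10.1.3, where the event is "first objective documentation of progressive disease (distant or local) or death".

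**The concern.** Radiation follows up to 8 FOLFIRINOX cycles of 14 days each (5.2, 6.2.1), that is up to 8 x 14 = 112 days, or 16 weeks, without delays. During that time the patient is at risk in the local control analysis, but there is no field in which a recurrence could occur. If the primary grows on chemotherapy and the patient leaves the study, the most direct form of local failure is not an event under 10.1.5.

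The result would be a local control rate that omits some of the worst local outcomes while keeping those patients in the analysis set. The same scan could also be a local progression for PFS and a non-event for local control, and a reader of the results could not see why.

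**Working it through.** **Step 1. Follow the text for each type of patient.** Under 10.3.2 the primary tumor is the target lesion, and under 10.5.1.3 an increase of at least 20% in its longest diameter is progression. Sections 5.4 and 5.6 make progression a criterion for ending treatment and for removal from study. Section 5.5 then limits follow-up to survival.

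| Patient | Field exists? | Local event under 10.1.5? | Handling under 14.4 |
|---|---|---|---|
| Primary progresses on FOLFIRINOX, not yet or never irradiated | No | No | Censored at last known local control |
| Irradiated, not resected, primary later grows | Yes; the gross primary is in the target volume (5.2.6.1) | Ambiguous: depends on whether regrowth of an unremoved tumor is a recurrence | Event or censored, by reading |
| Resected, relapse inside the field | Yes | Yes | Event |
| Resected, relapse outside the field | Yes | No | Censored; an in-field definition is a legitimate choice here |

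In the first row censoring happens because local control was lost. Kaplan-Meier assumes that censored patients have the same later risk as those still under observation. Here that assumption fails by construction, and the estimate moves upward.

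**Step 2. Are such patients expected?** Section 14.2 keeps patients who miss surgery because of progression or other reasons in the primary denominator. In the largest borderline-resectable series cited in 2.2.3, 66/160 = 41% were resected. For 50 patients this gives 0.4125 x 50 = 20.6, so about 21 resected and 29 not. That series used mixed regimens, mostly off protocol, and serves only to set a scale.

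**Step 3. Size, on assumed data.** The plan states no local control figure, so there is none to reproduce. Assumptions:

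- 50 patients, 21 resected, with in-field recurrences at 10, 14 and 17 months; the other 18 are followed beyond 24 months.
- 29 unresected. L of them have local progression, evenly spaced over months 3 to 9. The other 29 - L are censored evenly over months 3 to 12 without local progression.
- Not counted: the L patients are censored 2 months before progression. Counted: they are events at progression.

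The formula is S(24) = product over event times of (1 - d/n), with d events among n at risk. For L = 3:

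- Not counted: (26/27)(19/20)(18/19) = 0.867.
- Counted: (49/50)(39/40)(30/31) x (26/27)(19/20)(18/19) = 0.925 x 0.867 = 0.801.

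| L of 29 | Not counted | Counted | Difference (points) |
|---|---|---|---|
| 3 (10%) | 86.7% | 80.1% | 6.5 |
| 9 (about 30%) | 86.5% | 68.1% | 18.5 |
| 14 (about 50%) | 86.4% | 58.9% | 27.5 |

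Differences are taken before rounding. The "not counted" column applies the narrowest reading to all L patients. If in-field growth in irradiated, unresected patients is accepted as recurrence, some of the L become events and the gap shrinks.

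**Step 4. Primary endpoint.** The rule in 14.2 (at least 16 of 50) gives an exact binomial type 1 error of 0.031 at 20% and power of 0.904 at 40%, matching the stated 3% and 90%. It does not use local control.

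**The case against.** The strongest reply is that 14.4 never adopts the in-field restriction. It speaks of local failure, does not cite 10.1.5, and could be meant more broadly; the group's earlier report grouped failure with progression (2.2.5: "There have been 2 local failures/progression in ALL patients"). This is fair: the link between the two sections is an inference. But without the link the endpoint has no event definition at all, and with it the definition excludes progression before radiation. Either way the text has to be settled before analysis.

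Several stronger readings are tempting, and the documents do not support them.

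- *No unresected patient can have the event.* An irradiated patient has a field containing the primary, and regrowth there could be read as recurrence.
- *Such patients are carried as locally controlled.* They are censored at the last date of known local control. The fault is informative censoring.
- *A crude contrast over 50 patients gives the size.* The plan uses Kaplan-Meier, and any counts put in would be assumed.
- *Event status depends on protons or photons.* Section 5.2.6.1 gives one description of the target volumes for both.
- *The definition breaks comparability with the earlier in-house figure.* That study enrolled resectable patients, which already limits comparison, and its event definition is not in the documents.

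It also stands that local control is one of ten secondary objectives with no decision threshold, and that PFS already captures local progression in all treated patients.

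**Conclusion.** The point holds for progression of the primary before or without radiation: read literally, the plan censors it, and estimated local control is biased upward. For irradiated but unresected patients the text is ambiguous and needs a decision. For resected patients an in-field definition is defensible.

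The direction follows from the text; the size does not. The gap of about 7 to 28 percentage points at 24 months rests on assumed event counts and times, on a resection share borrowed from another series, and on the narrow reading for every unresected patient with local progression. Objective 1.3.7 cannot be interpreted clearly until the event is defined. The primary endpoint and its decision rule are unaffected.

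**What to change.** In 10.1.5, and by cross-reference in 14.4, define local failure once for all treated patients as the first of:

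1. objective progression of the primary tumor (10.5.1.3) before or without resection, whether or not radiation was given; or
2. local recurrence after resection.

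Record for each failure whether it was in or out of field, so that an in-field rate can still be reported alongside.

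The cost is a change of wording in two sections. PFS already requires local progression to be documented, and the study calendar (section 9) schedules restaging scans during FOLFIRINOX. There are two downsides. The local control figure will be less favourable. And for unresected patients, imaging after restaging is limited to what is done to document PFS: the calendar lists later scans only under post-operative follow-up, and 5.5 reduces follow-up to survival after progression. The report should state that limit.

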10.2 Definitions

10.2.1 Evaluable for toxicity. All participants who receive at least one dose of study treatment will be evaluable for toxicity from the time of their first treatment.

10.2.2 Evaluable for objective response. Only those participants who have measurable disease present at baseline, have completed at least 4 cycles of induction chemotherapy, and have had their disease re-evaluated will be considered

evaluable for response. These participants will have their response classified according to the definitions stated below. (Note: Participants who exhibit objective disease progression or die prior to the end of induction chemotherapy will also be considered evaluable.)

10.3 Disease Parameters

10.3.1 Measurable disease. Measurable disease is the presence of at least one (1) lesion that can be accurately measured in at least one dimension with longest diameter ≥ 20 millimeters (mm) using conventional techniques (CT, MRI, x-ray) or ≥ 10 mm with spiral CT scan. Measurable lesions must be at least 2 times the slice thickness in mm. All tumor measurements must be recorded in millimeters (or decimal fractions of centimeters).

10.3.2 Target lesions: The primary tumor is the target lesion.

10.4 Methods for Evaluation of Measurable Disease

All measurements should be taken and recorded in metric notation, using a ruler, calipers, or digital measurement tool. All baseline evaluations should be performed as closely as possible to the beginning of treatment and never more than 4 weeks before the beginning of the treatment.

The same method of assessment and the same technique should be used to characterize each identified and reported lesion at baseline and during follow-up. Imaging-based evaluation is preferred to evaluation by clinical examination when both methods have been used to assess the anti-tumor effect of a treatment.

10.4.1 Clinical lesions. Clinical lesions will only be considered measurable when they are superficial (e.g., skin nodules and palpable lymph nodes). For the case of skin lesions, documentation by color photography, including a ruler to estimate the size of the lesion, is recommended.

10.4.2 Conventional CT and MRI. These techniques should be performed with cuts of 10 mm or less in slice thickness contiguously. Spiral CT should be performed using a 5 mm contiguous reconstruction algorithm. This applies to tumors of the chest, abdomen,

and pelvis. Head and neck tumors and those of extremities usually require specific protocols.

10.4.3 Endoscopy, Laparoscopy. The utilization of these techniques for objective tumor evaluation has not yet been fully and widely validated. Their uses in this specific context require sophisticated equipment and a high level of expertise that may only be available in some centers. Therefore, the utilization of such techniques for objective tumor response should be restricted to validation purposes in reference centers. However, such techniques may be useful to confirm complete pathological response when biopsies are obtained.

10.4.4 Cytology, Histology. These techniques can be used to differentiate between partial responses (PR) and complete responses (CR) in rare cases (e.g., residual lesions in tumor types, such as germ cell tumors, where known residual benign tumors can remain). The cytological confirmation of the neoplastic origin of any effusion that appears or worsens during treatment when the measurable tumor has met criteria for response or stable disease is mandatory to differentiate between response or stable disease (an effusion may be a side effect of the treatment) and progressive disease.

10.5 Response Criteria

10.5.1 Evaluation of Target Lesions

10.5.1.1 Complete Response (CR): Disappearance of all target lesion.

10.5.1.2 Partial Response (PR): At least a 30% decrease in the sum of the longest diameter (LD) of target lesion, taking as reference the baseline sum LD.

10.5.1.3 Progressive Disease (PD): At least a 20% increase in the sum of the longest diameter (LD) of target lesion, taking as reference the smallest sum LD recorded since the treatment started or the appearance of one or more new lesions (new lesions must be > slice thickness).

10.5.1.4 Stable Disease (SD): Neither sufficient shrinkage to qualify for PR nor sufficient increase to qualify for PD, taking as reference the smallest sum LD since the treatment started.

10.5.1.5 Unknown (UN): Assessment of target lesions cannot be made due to insufficient or unevaluable data. In this case, a concise explanation must be given.

Note: If tumor response data is missing for target lesions, the overall assessment must be UN unless there is new disease that would result in an overall assessment of PD. However, if there is missing or unevaluable data for non-target lesions, but data is available for all target lesions, the overall response for that time point will be assigned based on the sum LD of all target lesions. Additionally, the assessment of CR cannot be made if there is missing or unevaluable data for non-target lesions. In this case, the overall assessment would be PR.

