5.6 Criteria for Removal from Study

Participants will be removed from study when any of the criteria listed in Section 5.4 applies. The reason for study removal and the date the participant was removed must be documented in the study-specific case report form (CRF). Alternative care options will be discussed with the participant.

In the event of unusual or life-threatening complications, participating investigators must immediately notify the Principal Investigator [name]. at [REDACTED]

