14 STATISTICAL CONSIDERATIONS

14.1 Study Design/Endpoints

This is a single-arm, phase II study to investigate the preoperative administration of FOLFIRINOX chemotherapy and accelerated short-course radiation therapy in patients with borderline-resectable adenocarcinoma of the pancreas.

The primary endpoint of this study is R0 resection rate determined by final pathology of the surgical specimen. The previously studied approach involved four months of induction gemcitabine followed by six weeks of neoadjuvant 5-FU-based chemoradiation (50.4 Gy). Our internal data support a historical R0 resection rate of 20% for patients with resectable

disease who received induction chemoradiation (CRT) (8 of 40) or induction chemotherapy followed by chemoradiation (C-CRT) (6 of 30). In a retrospective surgical series at MGH, median tumor size was 29 mm for the CRT group and 35 mm for C-CRT group. Among patients considered 'borderline resectable' upfront (n = 24), 5 of 24 = 21% had eventual margin-negative resection (or 7 of 24 = 29%, if < 1 mm is considered as a negative margin / R0 resection).

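### Progression is a 20% rise from the nadir of one diameter with no millimetre minimum, so a 3-5 mm change in a small primary is a PFS event

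*Combined protocol and SAP*

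**What the plan says.** Section 10.5.1.3 calls progressive disease on "At least a 20% increase in the sum of the longest diameter (LD) of target lesion". New lesions are the other route to it. The comparison value for growth is the nadir: "taking as reference the smallest sum LD recorded since the treatment started". Section 10.3.2 states that "The primary tumor is the target lesion", and 10.1.1 that "Changes in only the largest diameter (unidimensional measurement) of the tumor lesions are used in the RECIST criteria". The sum is therefore a single number.

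For new lesions 10.5.1.3 adds a size condition, "new lesions must be > slice thickness". It sets none for growth of the primary. Section 10.4.2 says "Spiral CT should be performed using a 5 mm contiguous reconstruction algorithm", and allows conventional CT or MRI cuts of up to 10 mm. Section 10.6 plans no central radiology review, and no confirmatory scan is described.

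Under 10.1.3, documented progression is a PFS event. Section 9 lists two restaging scans before surgery, both during FOLFIRINOX. Disease progression is also the first stopping criterion in 5.4, and 5.6 says "Participants will be removed from study when any of the criteria listed in Section 5.4 applies".

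**The concern.** A purely relative rule becomes stricter in millimetres as the tumour gets smaller. The reference is the lowest earlier reading, which reading error biases downwards because the minimum of several noisy values tends to lie below the truth. With one lesion, errors cannot average out across a sum. A small upward reading after a small low one can then be recorded as progression in a tumour that has not grown.

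What is at stake is mainly PFS, a secondary endpoint: a false event enters the Kaplan-Meier estimate at the date of the second restaging. The same call also feeds the response classification and the exploratory biomarker analyses of response and time to progression in 14.4.

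**Working it through.** **Inputs from the documents.** The threshold is 20% from nadir (10.5.1.3); partial response is a 30% decrease (10.5.1.2); spiral CT reconstruction is 5 mm (10.4.2). For size, 14.1 reports that "median tumor size was 29 mm for the CRT group and 35 mm for C-CRT group". Those medians come from a retrospective surgical series and serve here only as a proxy for baseline.

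**Trigger in millimetres.** Rise needed = 0.20 x nadir. A nadir of 15 mm gives 3 mm, 20 mm gives 4 mm and 25 mm gives 5 mm. A floor of 5 mm therefore changes the rule only for nadirs below 25 mm.

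| Baseline | Shrinkage | Nadir | Rise for PD | Size at PD | Against baseline |
|---|---|---|---|---|---|
| 29 mm | 0% | 29.0 | 5.8 | 34.8 | +20% |
| 29 mm | 20% | 23.2 | 4.6 | 27.8 | -4% |
| 29 mm | 30% | 20.3 | 4.1 | 24.4 | -16% |
| 35 mm | 0% | 35.0 | 7.0 | 42.0 | +20% |
| 35 mm | 20% | 28.0 | 5.6 | 33.6 | -4% |
| 35 mm | 30% | 24.5 | 4.9 | 29.4 | -16% |

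Size at PD relative to baseline is 1.20 x (1 - shrinkage). It is below 1 once shrinkage exceeds 1 - 1/1.20 = 16.7%. The trigger falls below 5 mm once shrinkage exceeds 1 - 25/29 = 14% from 29 mm, or 1 - 25/35 = 29% from 35 mm.

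**False progression at a fixed true size.** Assume an unchanged tumour, independent normal reading error at the nadir and follow-up scans, and PD if the rise is at least 20% of the measured nadir.

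| True size | Error SD | As written | With 5 mm floor |
|---|---|---|---|
| 20.3 mm | 1.5 / 2.0 mm | 4.2% / 9.6% | 0.9% / 3.9% |
| 24.5 mm | 1.5 / 2.0 mm | 1.8% / 5.8% | 0.9% / 3.8% |
| 29 mm | 1.5 / 2.0 mm | 0.7% / 3.1% | 0.7% / 3.1% |

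**False progression across a cohort, second restaging.** Assumptions: baseline diameter lognormal with median 29 or 35 mm and log-SD 0.30; true shrinkage with mean 20% and SD 15%, set to zero where negative, so no tumour truly grows; error SD 1.5-2.0 mm. PD if the second restaging reading is at least 1.2 times the smaller of the two earlier readings.

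| Shrinkage time course | As written | With 5 mm floor |
|---|---|---|
| Half by each restaging | 0.3-2.4% | 0.1-1.0% |
| All by the first restaging, then flat | 2.5-9% | 0.6-3.6% |

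In each range the low end is 35 mm with SD 1.5 mm, and the high end is 29 mm with SD 2.0 mm. With SD 1.0 mm, the flat case gives about 1% or less as written and essentially none with the floor.

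**The case against.** A relative rise from nadir is a recognised form of rule, and the plan has safeguards. A measurable lesion must be at least twice the slice thickness (10.3.1), and the same method and technique must be used at follow-up (10.4). Nothing in the documents links slice thickness to error in a measured diameter, so 5 mm is a convenient figure of the plan's own, not a derived one. In the 14.1 group closest to this regimen, the 35 mm group, a 20% shrinkage leaves a trigger of 5.6 mm and the floor does nothing. PFS is a secondary, single-arm estimate with no hypothesis test. All of this stands and limits the size of the point. It does not supply the missing minimum, and neither does 10.1.1, which cites RECIST without a version.

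Two stronger readings are tempting, and the documents support neither.

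- **That the error falls mainly on responders.** In the cohort simulation, tumours with at least 30% true shrinkage make up 37-50% of false calls if shrinkage is complete by the first restaging, but only 2-5% if it is gradual. The documents do not say which applies.
- **That stable patients lose surgery and the primary endpoint loses power.** The rule of 16 of 50 has exact power 90.4% at a 40% R0 rate and type I error 3.1% at 20%, matching 14.2. If every patient had a second restaging and every false call cost a resection, power would be about 88-90% with gradual shrinkage and about 79-88% in the flat case. These figures are an upper bound on the loss. Section 5.2 says up to 8 cycles, so not everyone need reach a second restaging. Section 5.4 names disease progression without citing the 10.5.1.3 threshold, and the operative condition in 5.2.7.1 is absence of metastases, not a diameter. Any such bias would lower the R0 rate; it could not raise type I error.

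**Conclusion.** The gap is real and modest. For primaries with a nadir of 15-25 mm, the rule turns a 3-5 mm change in one locally read diameter into a PFS event, even when the tumour is below its baseline size. Under assumed reading-error SDs of 1.5-2.0 mm, between about 0.3% and 9% of patients with a second restaging and no true growth would be called progressive there. With a 5 mm floor it is about 0.1% to 3.6%. Where in that range the trial falls depends on the reading error and on how shrinkage is spread over the two restagings, and the documents give neither. The proxy sizes, their spread and the shrinkage distribution are also assumptions.

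No R0 power gain should be credited to a change confined to PFS and response. Whether a diameter-only progression removes a patient from study is left unclear by 5.4, 5.6 and 10.5.1.3 read together.

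**What to change.** In 10.5.1.3, for the PFS and response endpoints, require both a 20% increase from nadir and an absolute increase of at least 5 mm in the primary. Leave the new-lesion criterion as it is. This is one clause and uses diameters already recorded in millimetres.

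The cost is that true growth of at least 20% but under 5 mm, from a nadir below 25 mm, may be called one scan later. The floor reduces false calls but does not abolish them, because there is still no confirmatory scan or central review.

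Separately, the investigators should state whether disease progression in 5.4, and hence removal under 5.6, means the 10.5.1.3 definition, so that the three sections agree. This point does not say what the removal rule should be.
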